2.6.3 Secondary analysis/analysis of secondary variables

Similar ANCOVA models as in the primary analysis will be fitted for the secondary and other pharmacodynamic variables or endpoints.

In addition, descriptive statistics for secondary and other pharmacodynamic variables in raw data and in change from baseline will be provided by treatment group (Sotagliflozin doses or placebo) for assessment from Day 1 to Day 14. Plots of the means overtime (\pm SEM) will also be presented.

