### 14.7.3 Secondary analysis/analysis of secondary variables

Descriptive statistics for all secondary and other pharmacodynamic endpoints, as raw data and change from baseline will be provided by treatment. Similarly time profile plots of mean  $\pm$  SEM will be provided by treatment for all secondary and other pharmacodynamics endpoints.

For exploratory purposes, the main pharmacodynamic variables, change from baseline to Day 14 in hemoconcentration and plasma volume, will be analyzed using an analysis of covariance (ANCOVA) model with fixed terms for treatment and stratification factor of baseline patient status (diabetic, non-diabetic, ejection fraction status (reduced-preserved), and with baseline plasma volume as covariate. An estimate for the between-group difference in treatment mean changes and corresponding 2-sided 90% confidence interval (CI) will be calculated from the model. The main treatment comparison will be between the pooled treatment (200 mg and 400 mg) group and placebo which will be made at 1-sided  $\alpha$  0.05 (or equivalently, 2-sided  $\alpha$  0.10).

Similar ANCOVA models will be fitted for the secondary and other pharmacodynamic variables or endpoints.

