2.6.1 Description of pharmacodynamic variables

The following pharmacodynamic variables will be analyzed:

Primary PD variables

- Change in hemoconcentration from baseline to D14/EOT as assessed by changes in hematocrit, hemoglobin, albumin and total protein.
- Change in plasma volume in milliliters from baseline to D14/EOT as assessed by the indicator dilution method using ¹³¹I-labelled human albumin.

Secondary PD variables:

- Change in erythropoietin (mU/ml) from baseline to D14 measured by chemiluminescent enzyme-labelled immunometric assay
- Change in NT-proBNP (pg/mL) from baseline to D14 measured by standard electrochemiluminescence immunoassay

Other Exploratory PD endpoints

- Change in total body water (mL) from baseline to D14 as assessed by the indicator dilution method using deuterium oxide
- Change in uric acid (mg/dL) from baseline to 14 days as measured by standard assay
- Change in beta-hydroxybutyrate (μM) from baseline to 14 days as measured by standard enzymatic colorimetric assay
- Change in red cell mass (mL) from baseline to D14, as derived from measurements of plasma volume (assessed by the indicator dilution method using ¹³¹I-labelled human albumin) and hematocrit
- Change in total blood volume (mL) from baseline to 14 days, as assessed by the indicator dilution method using ¹³¹I-labelled human albumin
- Percentage of patients within 15% of ideal blood volume on study day 14
- Blood pressure (sitting, SBP and DBP) at day 14, compared to baseline

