2.6.2 Primary analysis

The main pharmacodynamic variables, change from baseline to Day 14 in hemoconcentration and plasma volume, will be analyzed using an analysis of covariance (ANCOVA) model with fixed terms for treatment and stratification factor of baseline patient status (diabetic, non-diabetic, ejection fraction status (reduced-preserved), and with baseline plasma volume as covariate. An estimate for the between-group difference in treatment mean changes and corresponding 2-sided 90% confidence interval (CI) will be calculated from the model. The main treatment comparison will be between the pooled treatment (200 mg and 400 mg) group and placebo which will be made at 1-sided $\alpha=0.05$ (or equivalently, 2-sided $\alpha=0.10$).

No multiplicity procedures will be applied as the study is exploratory in nature.

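### The ANCOVA for NT-proBNP and erythropoietin should name each analyte's own baseline as covariate, and a log-scale model should be prespecified beside the raw-change one

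*SAP*

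**What the plan says.** SAP 2.6.1 defines the secondary variables on the assay scale: "Change in NT-proBNP (pg/mL) from baseline to D14 measured by standard electrochemiluminescence immunoassay" and "Change in erythropoietin (mU/ml) from baseline to D14 measured by chemiluminescent enzyme-labelled immunometric assay". Protocol 10.1.1.2 and 14.7.1 use the same units.

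For the model, SAP 2.6.3 states "Similar ANCOVA models as in the primary analysis will be fitted" for these variables and the remaining PD endpoints. Protocol 14.7.3 says "Similar ANCOVA models will be fitted for the secondary and other pharmacodynamic variables or endpoints". The model referred to (SAP 2.6.2) has terms for treatment, diabetes status and ejection-fraction status, "and with baseline plasma volume as covariate". Its result is a difference in means: "An estimate for the between-group difference in treatment mean changes and corresponding 2-sided 90% confidence interval (CI) will be calculated from the model".

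SAP 2.6.3 also plans that "descriptive statistics for secondary and other pharmacodynamic variables in raw data and in change from baseline will be provided by treatment group", and SAP 2.9 includes the median, minimum and maximum among the descriptive statistics. Neither document names a log transformation, a ratio measure, a distribution check or an own-baseline covariate for these variables.

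**The concern.** There are two separate issues.

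**Covariate.** The useful adjustment for a change in NT-proBNP is baseline NT-proBNP, and likewise for erythropoietin. Both are scheduled for all patients on Day 1 and Day 14 (protocol 1.2 and 1.4). Plasma volume by labelled albumin is done only at sites equipped for it, and a patient may decline it and stay in the study (protocol 10.1.2). SAP 2.9 gives no method for filling in a missing plasma volume baseline. A literal model could therefore adjust for a weakly related variable and also drop patients whose secondary data are complete.

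**Scale.** Both endpoints are positive concentrations. If they are right-skewed and vary in proportion to their level, a few patients with high values dominate the mean change and the residual variance. A log-scale model would then detect a treatment effect more often from the same data.

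At stake is the information obtained on the trial's only two secondary objectives, in a study now planned at 64 patients.

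**Working it through.** **The plan's own figure.** No power is stated for NT-proBNP or erythropoietin. The only power statement (SAP 1.3) concerns plasma volume: 71% with 54 vs 27. The SAP attaches 0.47 L to a 10% reduction, so 9 points is 0.47 × 9/10 = 0.423 L. With SD 0.8 L the standardised effect is 0.423 / (0.8 × √(1/54 + 1/27)) = 2.243. Power at one-sided 0.05 is Φ(2.243 − 1.645) = 72.5% (71.9% by the t distribution), which agrees with the stated 71%. It does not bear on the secondary endpoints.

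**Inputs.** Group sizes are from protocol Table 1: pooled sotagliflozin 10 + 27 = 37, placebo 27. One-sided alpha 0.05 is from SAP 2.6.2. Everything else is assumed: log-normal values, log-scale SD 0.6 to 1.0, baseline-to-Day-14 correlation of logs 0.70 to 0.85, and treatment ratios of 0.70, 0.85 and 1.3.

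**Models compared**, each with treatment, diabetes and ejection-fraction terms:
- A (literal plan): Y14 − Y0, with a covariate unrelated to Y standing in for plasma volume.
- B: Y14 − Y0, with covariate Y0.
- C: ln(Y14/Y0), with covariate ln(Y0). The exponentiated treatment coefficient is a ratio of geometric means.

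**Why B improves on A without any skew.** With equal variances at both visits and correlation ρ, the residual variance is 2(1 − ρ)σ² unadjusted and (1 − ρ²)σ² with the own baseline. Their ratio is (1 + ρ)/2: 0.85 at ρ = 0.70 and 0.925 at ρ = 0.85.

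**Simulation at ratio 0.70**, 4,000 trials per setting (Monte Carlo standard error at most √(0.25/4000) = 0.8 points):

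| log-SD | correlation | A | B | C | B − A | C − B |
|---|---|---|---|---|---|---|
| 0.6 | 0.70 | 75% | 89% | 94% | 14 | 5 |
| 0.6 | 0.85 | 93% | 98% | 99.6% | 5 | 1.6 |
| 0.8 | 0.70 | 48% | 64% | 78% | 16 | 14 |
| 0.8 | 0.85 | 71% | 83% | 95% | 12 | 12 |
| 1.0 | 0.70 | 33% | 44% | 62% | 11 | 18 |
| 1.0 | 0.85 | 50% | 61% | 85% | 11 | 24 |

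Allowing for simulation error, B gains about 5 to 15 points over A, and C gains about 1 to 24 over B.

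**Other effects.** At ratio 0.85, C gains about 5 to 10 points over B. For an increase of 1.3, the direction protocol 4.2.3 expects for erythropoietin, C gains about 7 to 22. The covariate matters less there. In one run at 1.3, A / B / C were 79.0 / 81.6 / 88.7% at log-SD 0.5, 35.9 / 39.2 / 52.2% at 0.8, and 22.5 / 24.7 / 38.7% at 1.0, so B − A is only about 2 to 3 points.

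**Type I error.** With no effect, rejection rates were 4.8% to 5.6% for all three models.

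**Where the log model loses.**
- Skewed log-normal baseline (median 1), but additive shift and additive noise (shift 0.2 with SD 0.3, or 0.3 with SD 0.5): raw change had 71 to 83% power and the log model 57 to 68%, a loss of about 14 to 20 points.
- Symmetric data: 84.8% raw to 83.6% log (CV 0.2, ratio 0.9), and 84.8% to 78.2% (CV 0.3, ratio 0.85).

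An additive shift with multiplicative errors still favours the log model (53.2% to 92.6% at log-SD 0.8). The error structure matters as well as the skew.

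**The case against.** The strongest reply is that no quantitative input on these analytes comes from the documents, and that log-normal data with a multiplicative effect make the log model true by construction. That stands. A reader might infer that right skew by itself shows the raw analysis to be the wrong choice. The additive case refutes this, because the baseline there is just as skewed and the raw model wins.

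The word *similar* may be meant to let each endpoint carry its own baseline. That is a reasonable reading, so the documents do not establish that plasma volume will be used. They leave the choice open, and a prespecified plan should close it.

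The secondary objectives are exploratory, no multiplicity control applies, and medians are already planned, so outliers will be visible. All of this stands and limits the consequence. It does not remove the case for a covariate statement that needs no new data.

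The log model also answers a different question: a ratio of geometric means, not a difference in pg/mL or mU/mL. The gain is in power to detect an effect, not a tighter interval for the same quantity. Since the protocol defines both endpoints in assay units, the log analysis belongs beside the raw one.

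**Conclusion.** The point holds in two parts of unequal strength.

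The covariate part needs no distributional assumption. The only baseline covariate named is plasma volume, which is not measured in everyone, while each analyte's own Day 1 value is scheduled for all. Under the stated assumptions the own baseline is worth about 5 to 15 points of power at ratio 0.70, and less for an increase.

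The scale part is conditional. If values are log-normal with multiplicative effect and errors, the log model adds about 1 to 24 points at 0.70, about 5 to 10 at 0.85, and about 7 to 22 for an increase of 1.3. If shift and errors are additive, it loses.

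The documents do not support the stronger conclusions that the planned analysis is invalid or that the log model should replace it. Type I error is near 5% either way, and what is affected is power for exploratory secondary endpoints.

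**What to change.** 1. In SAP 2.6.3, state that the ANCOVA for each secondary and other continuous PD endpoint uses that endpoint's own Day 1 value as baseline covariate, in place of baseline plasma volume. Align protocol 14.7.3 if it is amended again.
2. For NT-proBNP and erythropoietin, prespecify an additional ANCOVA of ln(Day 14/baseline) on ln(baseline), with the same treatment and stratification terms, reported as a ratio of geometric means with a 90% CI. Keep the protocol-defined raw change and its descriptive tables.
3. Check the population wording at the same time. SAP 2.6 runs all PD analyses on the PD population, and SAP 2.2.1 requires valid main PD values at both visits. If that is read as requiring plasma volume, changing the covariate will not bring back patients without it.

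The cost is a few sentences and one extra model for each of two endpoints, with no new data. The SAP needs revision in any case, because it still describes 81 patients. The downside is a second effect measure to explain. Both changes should be made before unblinding so that the scale and covariate are not chosen after seeing the results.

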2.7 ANALYSIS OF SAFETY DATA

The summary of safety results will be presented by treatment group. All safety analyses will be performed on the safety population.

The safety analysis will be based on the review of descriptive statistics (summary tables) and individual data for vital signs, renal function, adverse events (AEs) and other clinical laboratory values and ECG parameters.

Adverse events will be coded using Medical Dictionary for Regulatory Activities (MedDRA), and the number of patients with Treatment-Emergent Adverse Events (TEAEs) will be summarized by treatment group. Potentially clinically significant abnormalities (PCSAs) for clinical laboratory, vital sign, and ECG data and out-of-normal range values for clinical laboratory data will be flagged and summarized in frequency tables. The PCSA values are defined as abnormal values considered medically important by the Sponsor according to predefined criteria/thresholds based on literature review for clinical laboratory tests, vital signs and ECG parameters.

For all safety data, the observation period will be divided into three segments:

- the **pretreatment period** is defined as the time between informed consent signature and the first IMP administration;
- the **TEAE (treatment emergent AE) period** is defined as the time from the first IMP administration up to approximately 5 days after the last IMP administration (approximately 5 times the half-life of sotagliflozin);
- the **post-TEAE period** is defined as the time starting after the TEAE period up to the final study follow up telephone check.

2.7.1 Adverse events

2.7.1.1 Definitions

Adverse events will be coded to a “Preferred Term (PT)” and High Level Group Term (HLGT)”, “High Level Term (HLT)” and primary “System Organ Class (SOC)” using the Medical Dictionary for Regulatory Activities (MedDRA, version currently in use by the sponsor at the time of database lock). Their severity will be graded according NCI-CTCAE v4.03.

They will be classified into predefined standard categories according to chronological criteria:

- Pretreatment AEs: AEs that occurred, worsened or became serious during the pretreatment period.

- Treatment emergent AEs (TEAEs): AEs that occurred, worsened or became serious during the TEAE period.
- Post-TEAEs: AEs that occurred, worsened or became serious during the post-TEAE period.

TEAEs will be assigned to the treatment received at the time of the AE onset.

If the onset date (or time) of an AE (occurrence, worsening or becoming serious) is incomplete or missing, then the AE will be considered as a TEAE unless a partial date (or time) shows it as a pre- or post-treatment event

All AEs reported in the study will be listed, sorted by treatment group, subject, onset date and time.

2.7.1.2 Treatment-emergent adverse events

The following TEAEs summaries will be provided by treatment for the safety population:

- Overview of TEAEs: number and percentage of patients with any TEAE, any TEAE of special interest, any severe TEAEs, any serious TEAE, any TEAE leading to death (if any occurred), and any TEAE leading to permanent treatment discontinuation.
- Summary of TEAEs by primary SOC and PT:
 - number and percentage of patients with at least one TEAE;
 - number of occurrences of TEAEs.

Patients presenting TEAEs will be listed sorted by treatment group primary SOC and PT.

2.7.1.3 Deaths, serious, and other significant adverse events

Any deaths, serious and other significant AEs will be listed.

2.7.1.4 Adverse events leading to treatment discontinuation

Any AEs leading to permanent treatment discontinuation will be listed.

2.7.1.5 Adverse events of special interest

Adverse event of special interests (AESI) for this study are defined as follows:

- Pregnancy occurring in a female patient included in the clinical trial or in a female partner of a male patient entered in the clinical trial. It will be qualified as an SAE only if it fulfills one of the seriousness criteria.
 - In the event of pregnancy in a female patient, IMP should be discontinued,
 - Follow-up of the pregnancy in a female patient or in a female partner of a male patient is mandatory until the outcome has been determined.

- Symptomatic overdose (serious or nonserious) with IMP/non investigational medicinal product (NIMP)
 - A symptomatic overdose (accidental or intentional) with the IMP/NIMP is an event suspected by the Investigator or spontaneously notified by the patient and resulting in clinical symptoms and/or signs accompanied by administration of more than twice the intended daily dose within a 24-hour period. It will be recorded in the e-CRF as an AESI with immediate notification “Symptomatic OVERDOSE (accidental or intentional)” in all cases and will be qualified as an SAE only if it fulfills the SAE criteria.

(Please note that an Asymptomatic overdose with the IMP/NIMP, accidental or intentional, defined as administration of more than twice the intended daily dose within a 24-hour period, without clinical symptoms and/or signs, either suspected by the Investigator or spontaneously notified by the patient, not based on accountability assessment. It will be recorded as an AE “Asymptomatic OVERDOSE, accidental or intentional.”)

- ALT increased > 3X ULN

A summary of TEAEs reported as AESI (number and percentage of patients and the number of events) will be provided by AESI category and PT, sorted by decreasing incidence of PT within each AESI category.

2.7.2 Clinical laboratory evaluations

Baseline definition

The values to be used as the baselines will be the Day 1 predose assessment values. If any of the scheduled baseline tests are repeated for any subject, the last rechecked values will be considered as baselines, provided they were done before the first IMP administration.

Abnormalities analyses

For parameters with laboratory ranges and/or abnormality criteria (PCSA), analysis will be performed using all post-baseline assessments done during the TEAE period, including all unplanned and rechecked values. Counts of patients with PCSAs according to baseline status will be presented by treatment. The same type of summary tables will be provided for out-of-normal laboratory range values.

Descriptive statistics and plots

Raw data and changes from baseline will be summarized in descriptive statistics for all endpoint parameters, by treatment and scheduled time of measurement.

Additionally, graphs over time for these parameters will be presented plotting mean +/- SD by treatment.

PCSA Listings

A listing of individual data from patients with post-baseline PCSAs will be provided; values will be flagged when outside the laboratory limits and/or when reaching the PCSA criteria.

A listing of liver function data for subjects experiencing at least one of the following situations will be provided:

- ALT > 3ULN and total bilirubin > 2ULN during the study, with at least one of them being post first dose, irrespective of the definition of the TEAE period;
- Conjugated bilirubin > 35% of Total bilirubin and Total bilirubin > 1.5 ULN, on the same sample post first dose, irrespective of the definition for the TEAE period.

If any, a listing related to increase in ALT ≥ 2 ULN will be provided, including notably the information on drug intake, medical and surgical history, alcohol habits, and trigger factors, event details with ALT values, associated signs and symptoms.

Out-of-normal range definitions and unscheduled laboratory tests, if any, will be listed.

2.7.3 Vital signs

Heart rate (HR), systolic and diastolic blood pressures (SBP and DBP) will be analyzed as raw parameter value (for supine/sitting and standing positions), change from baseline (for supine or sitting position only) and as orthostatism parameter (standing-sitting/supine parameter values).

Body weight will be analyzed as raw parameter value and percent change from baseline and BMI will be analyzed as raw parameter value.

Baseline definition

The values to be used as baselines will be the Day 1 pre-dose assessment values. If any of the scheduled baseline tests are repeated for any subject, the last rechecked values will be considered as baselines, provided they were done before the IMP administration of the respective treatment phase, and in the same condition.

Abnormalities analyses

For all parameters, analysis will be performed using all post-baseline assessments done during the TEAE period, including all unplanned and rechecked values. Counts of patients with PCSAs will be presented by treatment, regardless of the baseline status.

Descriptive statistics and plots

For heart rate and blood pressures, raw data (supine/sitting and standing positions) and changes from baseline (supine/sitting position only) will be summarized in descriptive statistics by treatment and scheduled time of measurement.

For body weight, raw data and percent change from baseline will be summarized in descriptive statistics by treatment and scheduled time of measurement.

Additionally, graphs over time will be presented plotting mean +/- SD by treatment.

PCSA Listings

A listing of individual data from patients with post-baseline PCSAs will be provided; values will be flagged when reaching the PCSA criteria.

2.7.4 Electrocardiogram

ECG parameters (HR in bpm, QTc, QT, QRS and PR in msec) will be derived from the ECG obtained in hospital or during Visit days as per schedule of events. All parameters will be analyzed as raw data and absolute change from baseline. In addition, for the abnormalities analysis, PR and QRS will be also analyzed as percent change from baseline.

Baseline definition

The values to be used as baselines will be the Day 1 predose assessment values. If any of the scheduled baseline tests are repeated for any subject, the last rechecked values will be considered as baselines, provided they were done before the IMP administration of the respective treatment phase, and in the same condition.

Abnormalities analyses

For all parameters, analysis will be performed, using all post-baseline assessments done during the TEAE period, including all unplanned and rechecked values. Counts of patients with PCSAs will be presented by treatment, regardless of the baseline status.

Descriptive statistics and plots

ECG parameters (raw data and absolute change from baseline) will be summarized in descriptive statistics by treatment and scheduled time of measurement.

Additionally, graphs over time will be presented plotting mean +/- SD by treatment.

Listings

Following listings will be produced, using all data, including rechecked or unplanned values.

- A listing of individual data of subjects with any post-baseline PCSAs will be provided; raw data and absolute or percent change from baseline will be displayed depending on the parameter and values will be flagged when reaching the limits of the PCSA criteria;
- In addition, subjects with QTc/QTcB/QTcF >480 ms and/or change from baseline in QTc/QTcB/QTcF >60 ms will also be listed separately, using all post-dose timepoints.

- A listing of subjects with at least one abnormality in qualitative assessment (ie, abnormal 12-lead ECG) after the 1st dosing will be also provided.

